7.2. Study Objectives

7.2.1. Primary objectives

In the real life setting:

- to assess the impact of AXI in 2nd line post-SU on progression free survival (PFS) and on time to treatment failure (TTF) for patients with adv/mRCC
- to assess the impact of the SU-AXI sequence on combined PFS and TTF for patients with adv/mRCC

7.2.2. Secondary objectives:

In the real life setting:

- to assess the objective response rate (ORR) for adv/mRCC patients receiving AXI in 2nd line post SU,
- to describe usage of flexible dosing of AXI in these patients in terms of dosing change, dosing schedules and the average dose received during the AXI period treatment,
- to assess the proportion of titrated patients within adv/mRCC patients receiving AXI in 2nd line post SU,
- to assess the impact of titration on PFS for adv/mRCC patients receiving AXI in 2nd line post SU,
- to assess OS (OS median and 24-month OS) for adv/mRCC patients receiving SU in first line followed by AXI in 2nd line,
- to assess the time to strategy failure (TSF) for adv/mRCC patients receiving the SU-AXI sequence,
- to assess PFS and OS for the combined 1st line SU 2nd line sequences according to the second line post SU (TKI, m TOR),
- to describe safety and tolerability of patients receiving the SU-AXI sequence,
- to measure quality of life (QoL) in patients receiving AXI in 2nd line post SU.

8. - RESEARCH METHODS

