8.1.1. Study endpoints

Primary endpoints:

Progression Free Survival (PFS):

- PFS for patients with adv/mRCC receiving AXI in 2nd line post SU as defined as the time from when the patient receives the first dose of AXI to the time of progression or death due to any cause, whichever occurs first
- Combined PFS for patients with adv/mRCC receiving the SU-AXI sequence as defined
 as the time from when the patient receives the first dose with SU in first line, until
 progression or death due to any cause with AXI in 2nd line, whichever occurs first during
 the SU-AXI sequence

(Time to Treatment Failure) TTF:

- TTF for the AXI 2nd line as defined as from when the patient receives the first dose of AXI to the time of AXI discontinuation (date completed by the physician).
- TTF for the SU-AXI sequence as defined as the time from when the patient receives the first dose with SU in first line to the time of AXI discontinuation (date completed by the physician).

Secondary endpoints:

- Objective Response Rate (ORR) for adv/mRCC patients receiving AXI in 2nd line post SU defined as the percentage of patients with confirmed complete response (CR) or confirmed partial response (PR) according to RECIST criteria v1.1.
- Overall survival (OS) for adv/mRCC patients receiving SU in first line followed by AXI in 2nd line as measured from date of first SU dose to the date of death of any cause. The OS median and the overall survival at month 24 (24 month OS) will be measured.
- Time to strategy failure (TSF) for patients receiving the SU-AXI sequence is defines as the time from when the patient receives the first dose with SU in first line to the time of AXI discontinuation (date completed by the physician) without the time between discontinuation of SU and start of AXI.
- Description of real life usage of flexible dosing across Europe with description of treatment schedules (dosing change, dosing schedule, average dose received during the period treatment)

- Proportion of titrated patients: titration is defined as described in the SmPC. A patient is considered as titrated when an AXI dose increase is maintained for at least 4 weeks.
- PFS for titrated and non-titrated patients when they receive AXI in 2nd line post SU
- Efficacy parameters (PFS, OS) for the combined 1st line SU 2nd line sequences according to the second line post Sunitinib (other than SU-AXI):
 - SU in 1st line other TKI in 2nd line (sorafenib, pazopanib)

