8.2. Setting

The study will enroll patients according to the eligibility criteria in participating countries across Europe. The recruiting centers will be representative of each country involved in terms of care management systems, of size and of practices (at least when performing feasibility).

Any patient who meets the eligibility criteria will be invited to participate in the study with no selection by the investigators. The enrollment visit will be performed at the time of the patients' inclusion, after the patients' acceptation of enrollment in the study.

Data will come from medical records and will be collected in routine clinical practice. The enrollment visit will comprise a first section on patients' eligibility for every patient whatever pool they belong to and a second section depending on the treatment started (SU or AXI) at the inclusion.

For patients enrolled in the study when AXI is started as a 2^{nd} line therapy, a retrospective section will be completed at patients' inclusion, to collect data on SU 1^{st} line treatment.

For patients who start AXI when SU is discontinued during the study, the AXI initiation visit will resume baseline data that need to be updated.

Follow-up will be ensured during visits in the context of usual patients' care management (non-interventional study). No visits will be required by the protocol of the study. As long as the

patients are treated with SU or AXI, every visit to the center will be recorded. In accordance with ESMO guidelines and physicians clinical practice is real life, follow-up visits are approximately expected:

- during SU treatment: every 6 weeks (every cycle) with tumor assessment approximately every 3 months with respect to the clinical practice
- during AXI treatment: every 4 weeks (every cycle) with tumor approximately assessment every 2 months with respect to the clinical practice

[figure not shown]
When patients come off SU treatment (i.e. are not receiving AXI) or come off Axitinib (after receiving the SU-AXI sequence) they will be followed up every 6 months (separate form) for survival until the end of the study.

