8.7.1. Efficacy Analysis

Progression-Free Survival (PFS)

Combined PFS of the SU-AXI sequence is defined as the time from when the patient receives the the first dose with SU in first line, until progression or death due to any cause with AXI in 2nd line, whichever occurs first during the SU-AXI sequence. PFS in patients receiving AXI in 2nd line is defined as the time from when the patient receives the first dose of AXI to the time of progression or death due to any cause, whichever occurs first.

Patients who remain progression free at the end of AXI treatment will be evaluated until death, disease progression or the start of a new anticancer therapy.

For the primary endpoints, PFS will be assessed using the Kaplan-Meier method. This method will be applied to derive, survival curves, median event time and a 95% confidence interval for the median.

Kaplan-Meier estimates will also be provided for sub-group analysis of interest:

- Titrated and non-titrated patients, defined in the following section (titration description section), receiving AXI in 2nd line
- Patients receiving AXI in 2nd line post SU depending on the response to SU in 1rst line.
- Country cohorts where feasible (pool size)
- SU 2nd groups depending on the 2nd line treatment :
 - O SU in 1st line- AXI in 2nd line,
 - o SU in 1st line other TKI in 2nd line (sorafenib, pazopanib)
 - O SU in 1st line / mTOR in 2nd line. (temsirolimus, everolimus)

Potential influences of baseline patient characteristics (eg, age, sex, MSKCC risk group) on the primary PFS will be evaluated by Cox proportional regression method.

Time to Treatment to Failure (TTF) and Time to Strategy Failure (TSF)

TTF for the AXI 2nd line is defined as from when the patient receives the first dose of AXI to the time of AXI discontinuation (date completed by the physician) whatever the reason for discontinuation is and whatever the following therapeutic strategy. In case of death while the patient is still treated with AXI, date of death will be considered as date of discontinuation.

TTF for the SU-AXI sequence is as defined as the time from when the patient receives the first dose with SU in first line to the time of AXI discontinuation (date completed by the physician).

TSF for SU-AXI sequence is defined as the time from when the patient receives the first dose with SU in first line to the time of AXI discontinuation (date completed by the physician) without the time between discontinuation of SU and start of AXI.

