8.7.2. Analysis of other Endpoints

Titration of Axitinib

Titration is defined as described in the Axitinib (Inlyta ®) SmPC [1] (the active version at the date of patient's AXI Initiation).

Treatment titration schedules (dose changes, average daily dose over the treatment (in mg), dosing schedule) will be described in patients receiving AXI. A non-titrated and a titrated group will be defined based on the changes in dosing and the titration duration set up. Reason for non-

titration will be identified (hypertension, Grade 3/4 Adverse Drug Reaction): patients will be considered as titrated when an AXI dose increase is maintained at least 4 weeks.

Quality of life

QoL will be measured via the questionnaire Functional Assessment of Cancer Therapy-Kidney Symptom Index 19 (FKSI-19) and the Mental Health (MH) and Role-Emotional (RE) domains of the SF-36 questionnaire.

QoL as measured by FKSI-19 will be the sum of the scores from the FKSI-19 questionnaire. FKSI-19 will be reported using means (with standard deviations and 95% confidence intervals) and medians at each assessment point, based on the observed values as well as changes from baseline. Similar statistics will be provided for the RE and MH domains of SF-36.

QoL will also be assessed according to the response to AXI.

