Current Axi	tinib do	sage						
(the CRF displa	ys the do	sage scheduled at t	he previou	s visit)				
Has the Axitinib	dosage or	schedule been chang	ged since th	ne last docume	ented visit (including during this vi	isit)?		
☐ Yes ☐ No								
II yes please sp	ecify char	iges:						
Date	Dose red	uction		Dose titration	on up			
	☐ Yes	new dosage		□ Yes	new dosage			
	□ No	☐ 7 mg/2x/day		□ No	□ 10 mg/2x/day			
(DD/MMADA)		☐ 5 mg/2x/day			□ 7 mg/2x/day			
(DD/MM/YY YY)		☐ 3mg/2x/day			☐ 5 mg/2x/day			
		☐ 2mg/2x/day			☐ 3mg/2x/day			
		□ Other: ᆜᆜmg	/2x/day		☐ Other: ☐☐mg/2x/day			
	Reason f	or dose reduction		Reason for d	ose titration up			
	☐ Intolera	ance		☐ Good tolerance ☐ Inefficacity				
	☐ Other,			□ Other,				
(new lines can	be added	f more changes ha	ve occurre	ed)				
		ily interrupted since I	ast visit?	l Yes L	□ No			
II yes please sp	ecity inter	ruptions :						
First day of interruption		Duration in days	If yes, ne	w schedule				
			☐ Advers	se events	☐ Radiotherapy			
(DD/MM/YYYY	′)		□ Surger	у	□ Other			
(new lines can	(new lines can be added if more than 2 interruptions occurred)							

Other treatments						
Additional anti-tumor	treatment (e.g. bisphos	sphonates, others	s)			
(the previous visit anti-tumor treatment table is displayed)						
Has additional anti-tumor treatment been changed since last visit (including during this visit) ? ☐ Yes ☐ No						
If yes please update the ta	ble:					
Medication	Dosage	Starting date	Status			
	11		☐ Ongoing ☐ Discontinued			
(trade name)	(dose) (unit)	(MM/YYYY)	End date : —] / —] —] — (MM/YYYY)			
	/		☐ Ongoing ☐ Discontinued			
(trade name)	(dose) (unit)	(MM/YYYY)	End date :			
			(MM/YYYY)			
(new lines can be added if	more than 2 medications	are received)				
Radiotherapy : Yes		□ No				
Comedications (other	than tumor therapy) :	(the previous visit	t comedication table is displayed)			
Have comedications been c	hanged since last visit (includ	ling during this visit)	? □ Yes □ No			
If yes please update the ta	ble:					
Drug name	Starting date	Status				
		□ Ongoing □ Di	scontinued			
	(MM/YYYY)		(MM/YYYY))			
	(MM/YYYY)	□ Ongoing □ Di				
	\	End date/	LLL (MM/YYYY))			
(new lines can be added if more, than 2 treatment's are received)						

Safety							
Has the patient experienced adverse events related to Sunitinib during the treatment course? ☐ Yes ☐ No							

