4.2 STATISTICAL DECISION RULES

No statistical test will be performed. Whenever relevant, a two-sided 95% confidence interval will be provided.

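### PFS by titration status, counted from the first axitinib dose, is open to immortal-time bias because a patient becomes titrated only after holding a dose increase for 4 weeks

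*Protocol*

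**What the plan says.** Protocol 7.2 lists a secondary objective "to assess the impact of titration on PFS for adv/mRCC patients receiving AXI in 2nd line post SU", and SAP 2.2 repeats it. The matching endpoint in Protocol 8.1.1 is "PFS for titrated and non-titrated patients when they receive AXI in 2nd line post SU".

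Three elements of the plan combine:

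- **Time origin.** Axitinib PFS starts at the first axitinib dose (Protocol 8.1.1 and 8.7.1; SAP 6.1.1).
- **Group definition.** "A patient is considered as titrated when an AXI dose increase is maintained for at least 4 weeks" (Protocol 8.1.1). Protocol 8.7.2 says the same: "patients will be considered as titrated when an AXI dose increase is maintained at least 4 weeks".
- **Analysis.** Protocol 8.7.1 lists, among the subgroups for Kaplan-Meier estimates, "Titrated and non-titrated patients, defined in the following section (titration description section), receiving AXI in 2nd line".

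Scans are left to routine care. Protocol 8.2 expects, "during AXI treatment: every 4 weeks (every cycle) with tumor approximately assessment every 2 months with respect to the clinical practice". SAP 6.1.1 dates progression at the first tumour assessment showing it.

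The visible SAP defines no titrated subgroup in 5.4 and lists no PFS-by-titration analysis in 8.2.2. Its general tools are Kaplan-Meier, log-rank and Cox regression (8.1.2, 8.1.3), with baseline covariates (6.4). The available text of 8.2.2 stops in the middle of a list, so handling there cannot be excluded.

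**The concern.** Titration status cannot be known at time zero and cannot be reached before week 4. A patient whose dose would have been raised, but who progresses or dies first, is counted as non-titrated. A patient in the titrated group has normally been event-free up to the qualifying date, and that guaranteed time is credited to titration.

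The objective speaks of impact, and the rationale (Protocol 6, Gap 2) presents the study as evaluating what dose titration does to outcomes. The planned curves and medians could therefore show longer PFS in titrated patients when titration does nothing, with or without a test.

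**Working it through.** **The plan's own figure.** No precision or power is stated for this comparison. Table 2 gives an accuracy of 0.052 for all 350 SU-AXI patients. It reproduces: 1.96 × √(0.25/350) = 0.0524.

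**Inputs from the documents.** Median axitinib PFS after sunitinib 6.5 months, investigator-assessed (Protocol 6, Gap 1); n = 350 (Protocol 8.5); 4-week rule; scans about every 2 months; one month = 30.44 days (SAP 6.1.1).

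**Assumptions, because the documents give no figure.** No true effect; exponential PFS; 40% of patients are candidates for titration (range 30–50%); increase at week 2, 4 or 8, or spread over weeks 2–12 or 4–12; 0–20% of events off the scan schedule.

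**Closed form, progression dated continuously.** S(t) = 0.5^(t/6.5). Take an increase at week 4, so qualification at week 8, T = 56/30.44 = 1.84 months.

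- S(T) = 0.5^(1.84/6.5) = 0.822, so about 18% of candidates have their event first and are counted as non-titrated.
- Titrated median = T + 6.5 = 8.3 months.
- Non-titrated median m, with candidate share p, solves (1 − p)·S(m) / (1 − p·S(T)) = 0.5. For p = 0.3, S(m) = 0.5 × (1 − 0.3 × 0.822)/0.7 = 0.538 and m = 5.8 months.

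The result is 8.3 versus 5.8 months with no effect at all.

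**Why scan timing matters.** A scan at 2 months falls at 2 × 30.44/7 = 8.7 weeks. With strictly regular scans, a patient qualifying at week 6 or 8 does so before any progression can be recorded, so almost nobody is misclassified. A patient whose dose rises at week 8 qualifies at week 12, after the first scan, at which 1 − 0.5^(2/6.5) = 19% of patients are already recorded as progressed.

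**Simulated naive hazard ratios, titrated versus non-titrated, true value 1.00** (40% candidates, 200,000 patients per cell, titrated requiring observed PFS of at least the increase week plus 4):

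| Progression dated | Week 2 | Week 4 | Week 8 |
|---|---|---|---|
| Regular 2-monthly scans | 0.95–1.00 | 0.95–1.00 | 0.73–0.74 |
| Irregular scans (mean 2 months, SD 2.5 weeks) | 0.93–0.97 | 0.89–0.91 | 0.74–0.77 |
| Continuously | 0.80 | 0.75 | 0.67 |

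A repeat of these cells agreed to within 0.03. Spread-out increases give 0.74–0.81 with scans and 0.68–0.69 continuously. Example medians for weeks 4–12 with irregular scans are 9.2 versus 6.4–6.7 months. At 30–50% candidates the continuous-time ratio runs from 0.83 to 0.64. Adding administrative censoring moves it further from 1: at 30% candidates, from 0.78 to 0.75 for an increase at week 4 and from 0.71 to 0.66 at week 8.

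**Dilution.** If 25–50% of candidates count as titrated whatever their progression, the ratio for week 8 or weeks 4–12 is 0.80–0.88 with scans and 0.75–0.83 continuously.

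**If a log-rank test is run** (n = 350, nominal 5%), false rejection is 5–9% for week 2 or 4 with regular scans, 5–21% for week 2 or 4 with irregular scans, 47–82% for week 8 or spread increases with scans, and 50–95% continuously.

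**Alternatives under the same null.** A time-dependent Cox model gives a hazard ratio of 1.00 with 4.5–5.5% rejection. A week-16 landmark gives 1.00 with 4.3–5.7%.

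**The case against.** Several points on the other side have force.

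- **The size is not known.** It rests on the share and timing of titration, which the documents do not give; they refer to the SmPC for the definition. If every increase came by week 4 and scans were strictly 2-monthly, the distortion would be 0–5%. This stands as a limit. But this is routine care without mandated visits, and SAP 6.1.1 itself foresees patients without regular assessments.
- **The net direction is not certain.** The definition does not require the increase to precede progression, and the CRF axitinib follow-up form lists "Inefficacity" as a reason for titrating up. Such increases can dilute or oppose the bias. This also stands, and it is a further reason not to read the naive curves as an effect of titration.
- **The SAP may handle it in text not available here.** Protocol 8.7 allows the SAP to modify the plan, and SAP 5.4 and 8.2.2 may be incomplete in the available copy. So the claim is only that no handling is visible. The protocol's own analysis is explicit and unprotected.
- **The study is descriptive.** Protocol 8.5 says so, and SAP 4.2 states, "No statistical test will be performed". That removes the false-rejection figures if it is followed, but SAP 8.1.2 plans a log-rank test for subgroups of interest. Curves and medians are distorted either way.

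**Conclusion.** The concern holds. The time origin, the 4-week rule and the plain Kaplan-Meier comparison together allow immortal time to favour titrated patients. That the bias can arise follows from the definitions; its size does not. On the stated assumptions it ranges from negligible (early increases, regular scans) to a spurious hazard ratio of about 0.73–0.81 for later or spread increases with scan-dated progression, and 0.64–0.83 if progression were dated continuously. Increases made for inefficacy could shrink or oppose it. It affects one secondary objective; the primary PFS and TTF analyses are untouched. It should be fixed before analysis.

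**What to change.** In the SAP, specify for this objective:

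1. **A landmark Kaplan-Meier analysis** in patients on axitinib and event-free at a prespecified time, grouped by status at that time, with PFS counted from it. Week 16 is one example, since an increase by week 12 would have qualified by then. Add a second landmark as a sensitivity analysis.
2. **A Cox model for axitinib PFS** with titration as a time-dependent covariate that switches on when the 4-week criterion is met.
3. **Supporting rules.** Count only increases that precede progression. Adjust for baseline blood pressure or hypertension and for MSKCC risk, both collected at axitinib initiation. State that confounding by tolerance or inefficacy remains.

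Two related repairs: reconcile SAP 4.2 with 8.1.2 on testing, and report the proportion titrated by the 4-week definition beside the dose-increase proportion in SAP 8.2.3.

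The cost is SAP text and modest programming, because the CRF dates each dose change. The week-16 landmark kept 68–76% of patients in simulation (0.5^(3.68/6.5) = 0.675 in continuous time); patients who stop axitinib earlier without progression would lower that further. It drops early events and counts later titrations as non-titrated. Neither method removes confounding by indication.

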A number of publications support the hypothesis that dose titration of axitinib in a select group of patients who tolerate the drug at the standard starting dose may improve the efficacy [18-20].

Indeed, there is a variable level of drug exposure between patients and a significant percentage of patients are below the therapeutic drug threshold. Pharmacokinetic data suggest that normalization of plasma exposures can be achieved with dose titration [20, 21].

Clinical parameters for dose titration based on individual tolerability are useful for identifying patients with sub-therapeutic axitinib exposure at the 5 mg BID starting dose. Recent studies support an association between hypertension, Axitinib dose/plasma concentration and clinical outcome [22]. A retrospective analysis across 5 phase II studies of axitinib for the treatment of different solid tumor types shows that axitinib efficacy correlated with diastolic blood pressure \geq 90 mm Hg [23]. Recent results of a pharmacokinetic analysis also support axitinib dose titration to increase plasma exposure in patients who tolerate axitinib and demonstrate diastolic blood pressure as a potential marker of efficacy [20].

Axitinib, Inlyta[®]
A4061078 NON-INTERVENTIONAL STUDY PROTOCOL
ADONIS Amended V13
28 Sept 2017

In a randomized phase II clinical trial with axitinib for first-line metastatic RCC, the best response rate was obtained in patients with the highest rate of hypertension (82%) at baseline and thus who were not titrated. It suggests that these patients had adequate plasma exposure at the starting dose and that diastolic blood pressure could be considered as a marker of efficacy [24].

Dose increase or dose reduction of axitinib (Inlyta®) is labeled in the SmPC. The flexible dosing gives the physicians the option and flexibility to tailor the dose to each individual patient in order to optimize outcomes. Blood pressure appears as a potential predictive biomarker to define the suitable dose schedule. Though, the association between hypertension, Axitinib titration and clinical outcome needs to be further investigated.

ADONIS will allow assessing flexible dosing usage across Europe in real life and evaluate the impact of dose titration on the treatment outcomes of Axitinib in 2nd line mRCC patients post Sunitinib.

Gap 3:

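### The impact of axitinib titration on PFS rests on two unadjusted curves; the groups form for prognostic reasons, so confounding by indication can push the contrast either way

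*Protocol*

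**What the plan says.** **Objective.** Protocol 7.2.2 sets out "to assess the impact of titration on PFS for adv/mRCC patients receiving AXI in 2nd line post SU". Gap 2 of the rationale (section 6) presents this as one of the reasons for running the study, and SAP 2.2 repeats the objective.

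**Endpoint and definition.** Protocol 8.1.1 gives the matching secondary endpoint as "PFS for titrated and non-titrated patients when they receive AXI in 2nd line post SU", and defines the groups: "A patient is considered as titrated when an AXI dose increase is maintained for at least 4 weeks". The clock starts earlier. In 8.7.1, "PFS in patients receiving AXI in 2nd line is defined as the time from when the patient receives the first dose of AXI".

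**Analysis.** Section 8.7.1 lists, among the subgroups that get Kaplan-Meier estimates, "Titrated and non-titrated patients, defined in the following section (titration description section), receiving AXI in 2nd line". The only adjusted PFS analysis in the protocol is a Cox model of baseline characteristics, and titration is not named in it.

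**How patients reach each group.** On a first-line phase II trial, section 6 says that "the best response rate was obtained in patients with the highest rate of hypertension (82%) at baseline and thus who were not titrated", and reads this as adequate exposure at the starting dose. Section 8.7.2 says that the reason for non-"titration will be identified (hypertension, Grade 3/4 Adverse Drug Reaction"). On the axitinib follow-up form in Annex 1, the reasons for a dose increase are good tolerance, "Inefficacity" or other.

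**SAP.** Section 5.4 defines no titrated subgroup, 6.4 does not list titration as a covariate, and 8.2.2 lists no PFS by titration. Sections 6.3.1 and 8.2.3 give only the proportion of patients whose dose was increased.

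**The concern.** On the protocol's own account, the non-titrated group joins unlike patients: those with hypertension, who may do well; those with grade 3/4 reactions, who may do badly; and those with neither, who could have been titrated but were not. The titrated group is mixed too, because a dose raised for good tolerance and one raised for inefficacy point to different outlooks. A crude split then compares case mixes as much as dosing.

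If titration does nothing, the curves can still separate, and the sign depends on whether hypertension or toxicity dominates among non-titrated patients. The outcome part of Gap 2 would be answered by that mix. The limitations section (8.9) does not mention it.

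**Working it through.** **1. The plan's own precision figure.** Protocol 8.5 gives no figure for the titration contrast. Its Table 2 reproduces: 1.96 × √(0.25/350) = 0.0524, stated as 5.2%. That applies to all 350 SU-AXI patients. If 20% to 50% are titrated (assumption; 70 to 175 patients), the half-width in the titrated group is 1.96 × √(0.25/70) = 11.7 points to 1.96 × √(0.25/175) = 7.4 points.

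**2. Confounding alone, no titration effect.** The 6.5-month reference median is the investigator-assessed AXIS figure in section 6. Every share and every other median is an assumption. PFS is exponential with hazard λ = ln 2 / median, and follow-up is cut at 36 months. Per patient, the expected event fraction is F = 1 − exp(−36λ) and expected follow-up is F/λ. The crude hazard ratio is approximated by the titrated event rate divided by the non-titrated event rate.

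Worked case: 40% untitrated for hypertension (median 10), 10% for toxicity (median 5), and 50% who could be titrated, of whom 60% are. The non-titrated weights are 0.40, 0.10 and 0.20.

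- λ = 0.0693, 0.1386, 0.1066; F = 0.9175, 0.9932, 0.9785.
- Events: 0.3670 + 0.0993 + 0.1957 = 0.6620.
- Person-months: 5.295 + 0.716 + 1.835 = 7.846.
- Non-titrated rate 0.6620/7.846 = 0.0844; ratio 0.1066/0.0844 = 1.26.

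| Hypertension: share, median | Toxicity: share, median | Crude ratio, titrated vs not |
|---|---|---|
| 40%, 10 | 10%, 6.5 | 1.30 |
| 40%, 10 | 10%, 5 | 1.26 |
| 40%, 8.5 | 10%, 5 | 1.14 |
| 20%, 10.8 | 20%, 3.9 | 1.06 |
| 10%, 8.5 | 40%, 5 | 0.91 |
| 10%, 8.5 | 40%, 4 | 0.82 |

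In every row 60% of the patients who could be titrated are titrated. Cox fits to data simulated under the same assumptions agree to within 0.01.

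**3. The 4-week rule, kept separate.** A patient whose first increase falls at week 2 to 8 (assumption) must stay progression-free for 6 to 12 weeks, or 1.38 to 2.76 months, to count as titrated. With a 6.5-month median, 1 − exp(−0.1066 × 1.38) = 14% to 1 − exp(−0.1066 × 2.76) = 25% progress or die first and fall into the non-titrated group. With no confounding and 30% to 50% of patients intended for titration, simulation gives crude ratios of 0.63 to 0.84 under no effect. This part has a known direction. Combined with confounding over wider assumed mixes, the range was 0.62 to 1.53.

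**4. Test of an obvious repair.** Suppose all titrated patients are compared with non-titrated patients who had neither hypertension nor a grade 3/4 event. Assume 40% hypertensive (median 10), the rest with median 6.5, half of the rest titrated, no toxicity stratum and no titration effect. If 10% of hypertensive patients are titrated, titrated events are 0.04 × 0.9175 + 0.30 × 0.9785 = 0.3302 over 3.282 person-months, a rate of 0.1006 and a ratio of 0.1006/0.1066 = 0.94. At 20% and 30% the ratio is 0.90 and 0.87. If titration is unrelated to hypertension (30% in both), the crude ratio is 1.00 but this contrast gives 0.83. Applying the same restriction to both sides restores 1.00.

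**The case against.** **The study is descriptive.** Protocol 8.5 says so, the primary objectives use the same word, impact, in a non-controlled study, and neither document names a hazard ratio or test for titration. SAP 4.2 rules out testing, although 8.1.2 describes a log-rank test for subgroups. This stands in part. The ratios above measure how far the two curves can mislead; they are not planned outputs. But the objective asks for an impact, and two side-by-side curves will be read as the answer.

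**Some handling is planned.** Section 8.7.2 will identify reasons for non-titration, Table 1 labels several variables as potential confounders, and hypertension history is a candidate for the SAP's Cox model. This also stands in part. No PFS by reason is planned, the CRF pages shown have no field for the reason, and titration is not among the listed Cox covariates.

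**Stronger readings a reader might infer.**

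- That the SAP runs the crude contrast. Its visible text omits the analysis. That silence is weak evidence, because 8.2.2 breaks off at a colon.
- That the rationale names both reasons for non-titration. It names only hypertension; grade 3/4 reactions appear in 8.7.2. The evidence of better outcome is a response rate from a first-line trial, not second-line PFS.
- That all of Gap 2 fails. Describing how flexible dosing is used is unaffected.

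**Conclusion.** The concern holds for the titration-PFS objective. The only planned analysis in view is unadjusted, and the documents themselves show that the groups form for reasons linked to prognosis. The direction of the confounding cannot be fixed in advance, because the mix of hypertension and toxicity is not given. Its possible size, about 0.8 to 1.3 with no true effect, rests on assumed shares, assumed medians and exponential PFS; an even mix gives almost no distortion. The bias from the 4-week rule is separate and favours titrated patients, so correcting the timing alone would leave the confounding in place. A reader might conclude that the curves must understate, or must overstate, titration. The documents support neither.

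**What to change.** In Protocol 8.7.1 and SAP 8.2.2:

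1. Fix titration status at a pre-stated landmark, or treat it as time-dependent.
2. Show PFS of non-titrated patients separately by reason: hypertension, or antihypertensive treatment started or increased; grade 3/4 AE; neither. Show titrated patients by recorded reason for the increase.
3. If one titration estimate is given, apply the same hypertension and grade 3/4 AE restriction, assessed before titration or the landmark, to titrated and non-titrated patients alike, or adjust for these factors in both. Also adjust for MSKCC class, ECOG and sunitinib duration.
4. Report the result as an association, reword the objective to match, and add the confounding to section 8.9.

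Blood pressure, antihypertensive changes and reasons for increase already have CRF fields. Check first that axitinib AE grades are captured: the safety question on the axitinib follow-up form asks about events related to sunitinib, and the Annex 2 form as reproduced shows no grade field. The reason for non-titration would have to be derived.

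The cost is SAP and protocol wording plus derived variables. The price in the results is smaller groups, wider intervals and some residual confounding.
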